10.5. Appendix 5: Revised American College of Rheumatology Criteria for Diagnosis of GCA

2016 Revised American College of Rheumatology criteria for diagnosis of Giant Cell (Temporal) Arteritis^a. ([Salehi-Abari 2016](#)).

Entry Criteria

- Age at onset ≥ 50 years old
- Absence of exclusion criteria^b

Domain I Criteria

- New onset localized headache^c 1p
- Sudden onset of visual disturbances^c 1p
- Polymyalgia Rheumatica (PMR) 2p
- Jaw Claudication^c 1p
- Abnormal temporal artery^d up to 2p

Domain II

- Unexplained fever and/or anaemia 1p
- ESR ≥ 50 mm/hour^e 1p
- Compatible pathology^f up to 2p

^a In the presence of 3 points (p) or more out of 11 with at least one point belonging to domain I along with all entry criteria, the diagnosis of Giant cell arteritis can be established;

^b Exclusion criteria are including: ENT and eye inflammation, kidney, skin and peripheral nervous system involvement, lung infiltration, lymphadenopathies, stiff neck and digital gangrene or ulceration;

^c No other etiologies can better explain any one of the criteria;

^d Enlarged and/or pulseless temporal artery: 1.p./tender temporal artery: 1.p;

^e It must be ignored in the presence of PMR;

^f Vascular and/or perivascular fibrinoid necrosis along with leucocyte infiltration: 1.p. /and granuloma: 1.p.

10.6. Appendix 6: Hepatitis B Virus (HBV) Screening with HBV DNA Testing

Participants must undergo screening for HBV. At a minimum, this includes testing for HBsAg (HBV surface antigen), anti-HBs (HBV surface antibody), and anti-HBc total (HBV core antibody total):

- Participants who test negative for all HBV screening tests (ie, HBsAg-, anti-HBc-, and anti-HBs-) **are eligible** for this study
- Participants who test **negative** for surface antigen (HBsAg-) and test **positive** for core antibody (anti-HBc+) **and** surface antibody (anti-HBs+) **are eligible** for this study
- Participants who test **positive only for surface antibody** (anti-HBs+) **are eligible** for this study
- Participants who test **positive** for surface antigen (HBsAg+) **are NOT eligible** for this study, regardless of the results of other hepatitis B tests
- Participants who test **positive only for core antibody** (anti-HBc+) must undergo further testing for the presence of hepatitis B virus deoxyribonucleic acid (HBV DNA test). If the HBV DNA test is **positive**, the participant **is NOT eligible** for this study. If the HBV DNA test is **negative**, the participant **is eligible** for this study. In the event the HBV DNA test cannot be performed, the participant **is NOT eligible** for this study

Eligibility based on hepatitis B virus test results		Hepatitis B test result		
Action	Hepatitis B surface antigen (HBsAg)	Hepatitis B surface antibody (anti-HBs)	Hepatitis B core antibody (anti-HBc total)	
Include				
		+		
		+	+	
Exclude	+	or +	or +	
Require testing for presence HBV DNA*			+	

* If HBV DNA is detectable, exclude from the clinical study. If HBV DNA testing cannot be performed, or there is evidence of chronic liver disease, exclude from the clinical study.

For participants who **are not eligible for this study due to HBV test results**, consultation with a physician with expertise in the treatment of hepatitis B virus infection is recommended.

10.7. Appendix 7: Contraceptive and Barrier Guidance

Participants must follow contraceptive measures as outlined in Section 5.1, Inclusion Criteria. Pregnancy information will be collected and reported as noted in Sections 8.3.5, Pregnancy and 10.4, Adverse Events, Serious Adverse Events, Product Quality Complaints, and Other Safety Reporting: Definitions and Procedures for Recording, Evaluating, Follow-up, and Reporting.

Definitions

Woman of Childbearing Potential (WOCBP)

A woman is considered fertile following menarche and until becoming postmenopausal unless permanently sterile (see below).

Woman Not of Childbearing Potential

- **premenarchal**

A premenarchal state is one in which menarche has not yet occurred.

- **postmenopausal**

A postmenopausal state is defined as no menses for 12 months without an alternative medical cause. A high follicle stimulating hormone level (>40 IU/L or mIU/mL) in the postmenopausal range may be used to confirm a postmenopausal state in women not using hormonal contraception or hormonal replacement therapy (HRT), however in the absence of 12 months of amenorrhea, a single follicle stimulating hormone measurement is insufficient. If there is a question about menopausal status in women on HRT, the woman will be required to use one of the non-estrogen-containing hormonal highly effective contraceptive methods if she wishes to continue HRT during the study.

- **permanently sterile**

Permanent sterilization methods include hysterectomy, bilateral salpingectomy, bilateral tubal occlusion/ligation procedures, and bilateral oophorectomy.

Note: If the childbearing potential changes after start of the study (eg, a premenarchal woman experiences menarche) or the risk of pregnancy changes (eg, a woman who is not heterosexually active becomes active), a woman must begin a highly effective method of contraception, as described throughout the inclusion criteria.

If reproductive status is questionable, additional evaluation should be considered.

Contraceptive (birth control) use by men or women should be consistent with local regulations regarding the acceptable methods of contraception for those participating in clinical studies.

Typical use failure rates may differ from those when used consistently and correctly. Use should be consistent with local regulations regarding the use of contraceptive methods for participants in clinical studies.

Examples of Contraceptives

EXAMPLES OF CONTRACEPTIVES^a ALLOWED DURING THE STUDY INCLUDE:	
USER INDEPENDENT	
Highly Effective Methods That Are User Independent Failure rate of <1% per year when used consistently and correctly. 
 Implantable progestogen-only hormone contraception associated with inhibition of ovulation^b Intrauterine device (IUD) Intrauterine hormone-releasing system (IUS) Azoospermic partner (vasectomized or due to medical cause) (Vasectomized partner is a highly effective contraceptive method provided that the partner is the sole sexual partner of the woman of childbearing potential and the absence of sperm has been confirmed. If not, additional highly effective method of contraception should be used. Spermatogenesis cycle is approximately 74 days.) 	
USER DEPENDENT	
Highly Effective Methods That Are User Dependent Failure rate of <1% per year when used consistently and correctly. 
 Combined (estrogen- and progestogen-containing) hormonal contraception associated with inhibition of ovulation^b 
 oral intravaginal transdermal injectable Progestogen-only hormone contraception associated with inhibition of ovulation^b 
 oral injectable Sexual abstinence (Sexual abstinence is considered a highly effective method only if defined as refraining from heterosexual intercourse during the entire period of risk associated with the study intervention. The reliability of sexual abstinence needs to be evaluated in relation to the duration of the study and the preferred and usual lifestyle of the participant.) 	
NOT ALLOWED AS SOLE METHOD OF CONTRACEPTION DURING THE STUDY (not considered to be highly effective - failure rate of ≥1% per year)	

 Progestogen-only oral hormonal contraception where inhibition of ovulation is not the primary mode of action. Male or female condom with or without spermicide^c Cap, diaphragm, or sponge with spermicide A combination of male condom with either cap, diaphragm, or sponge with spermicide (double-barrier methods)^c Periodic abstinence (calendar, symptothermal, post-ovulation methods) Withdrawal (coitus-interruptus) Spermicides alone Lactational amenorrhea method (LAM) 	
a) Typical use failure rates may differ from those when used consistently and correctly. Use should be consistent with local regulations regarding the use of contraceptive methods for participants in clinical studies.	

- b) Hormonal contraception may be susceptible to interaction with the study intervention, which may reduce the efficacy of the contraceptive method. In addition, consider if the hormonal contraception may interact with the study intervention.
- c) Male condom and female condom should not be used together (due to risk of failure with friction).

Pregnancy During the Study

All initial reports of pregnancy in female participants or partners of male participants must be reported to the sponsor or designee by the study-site personnel within 24 hours of their knowledge of the event using the appropriate pregnancy notification form. Abnormal pregnancy outcomes (eg, spontaneous abortion, fetal death, stillbirth, congenital anomalies, ectopic pregnancy) are considered SAEs and must be reported using the Serious Adverse Event Form. Any participant who becomes pregnant during the study must discontinue further study intervention.

Follow-up information regarding the outcome of the pregnancy and any postnatal sequelae in the infant will be required.

10.8. Appendix 8: Protocol Defined 26-Week Glucocorticoid Taper

Table 3: Protocol Defined 26-Week Glucocorticoid Taper[#]

[figure not shown]
Week	Initial prednisone ⁺ dose at Randomization (*)			
	60-50 mg	49-40 mg	39-30 mg	29-20 mg
	Daily dose (mg/day)	Daily dose (mg/day)	Daily dose (mg/day)	Daily dose (mg/day)
0 ^{**}	60-50	49-40	39-30	29-20
1	50	40	30	20
2	40	35	25	20
3	35	30	20	17.5
4	30	25	20	17.5
5	25	20	17.5	17.5
6	20	17.5	17.5	15
7	17.5	15	15	15
8	15	15	15	15
9	12.5	12.5	12.5	12.5
10	12.5	12.5	12.5	12.5
11	10	10	10	10
12	10	10	10	10
13	9	9	9	9
14	8	8	8	8
15	7	7	7	7
16	6	6	6	6
17	6	6	6	6
18	5	5	5	5
19	5	5	5	5
20	4	4	4	4
21	4	4	4	4
22	3	3	3	3
23	3	3	3	3
24	2	2	2	2
25	1	1	1	1
26	0	0	0	0
27	0	0	0	0
28	Primary Endpoint Assessment Week 28			

- * Individual participants will be receiving different doses of prednisone (or equivalent) at specified time points, depending on their initial GC dose at randomization. Therefore, the tapering schedule indicates the required decrease in prednisone dose on a weekly basis, with the specific week varying by individual participant.

- ** The first week (Week 0) after randomization the participant will take their initial GC dose, and per Week 1 start with their taper in accordance with this table and their initial starting dose.
- + If the participant continues on GC other than prednisone or prednisolone, the Investigator should contact the Sponsor to ensure that the taper is appropriately adjusted for the GC equivalency compared with prednisone, using the Appendix 10 conversion table to convert the Prednisone Taper doses to the equivalent alternate glucocorticoid.
- # In countries where not all required tablet strengths are available to comply with the lower doses of the protocol-defined taper, where authorized (ie, HA and Ethics Committee approval in place), small variations in daily steroid dose of up to 0.5 mg/day are allowed to make the taper feasible. Sites that are impacted by this should reach out to the sponsor clinical team for further guidance before any participants start their taper. If tablets need to be cut in half or in quarters this should preferably be performed by site staff.

[figure not shown]
10.9. Appendix 9: Liver Safety: Suggested Actions and Follow-up Assessments

Guideline Algorithm for Monitoring, Assessment & Evaluation of Abnormal Liver Tests in Participants with no Underlying Liver Disease

Abbreviations: ALT = alanine transaminase; AST = aspartate transaminase, INR = international normalized ratio; SAE = serious adverse event; ULN = upper limit of normal, Tbili = Total bilirubin

Liver Chemistry Increased Monitoring Algorithm with Continued Study Intervention for Participants with ALT or AST $\geq 3\times$ ULN but $< 8\times$ ULN

Abbreviations: ALT = alanine transaminase; AST = aspartate transaminase, Tbili = total bilirubin; INR = international normalized ratio; SAE = serious adverse event; ULN = upper limit of normal, Tbili = Total bilirubin

^aIn participants whose liver function tests (ALT or AST) are $\geq 5\times$ ULN, medication should be interrupted until a decrease in liver function test is noted.

In those cases of liver function tests (ALT or AST) $\geq 5 \times$ ULN where a potential etiology other than guselkumab is identified, the study intervention may be interrupted for an extended period (>2 weeks) until a thorough assessment is performed by the investigator and Sponsor prior to the restart of study intervention. If liver function tests remain $\geq 5 \times$ ULN for 2 weeks and are considered related to study intervention, investigational treatment will be discontinued.

Phase 3-4 liver chemistry stopping criteria are designed to assure participant safety and to evaluate liver event etiology.

Liver Chemistry Stopping Criteria	
ALT /AST-absolute	ALT or AST $\geq 8 \times$ ULN
ALT /AST Increase	ALT or AST $\geq 5 \times$ ULN but $< 8 \times$ ULN persists for ≥ 2 weeks ALT or AST $\geq 3 \times$ ULN but $< 5 \times$ ULN persists for ≥ 4 weeks
Bilirubin^{1, 2}	ALT or AST $\geq 3 \times$ ULN and total bilirubin $\geq 2 \times$ ULN (or at least a doubling of direct bilirubin in known Gilbert's syndrome)
INR²	ALT or AST $\geq 3 \times$ ULN and international normalized ratio (INR) > 1.5, if INR measured
Cannot Monitor	ALT or AST $\geq 5 \times$ ULN but $< 8 \times$ ULN and cannot be monitored weekly for ≥ 2 weeks ALT or AST $\geq 3 \times$ ULN but $< 5 \times$ ULN and cannot be monitored weekly for ≥ 4 weeks
Symptomatic³	ALT or AST $\geq 3 \times$ ULN associated with symptoms (new or worsening) believed to be related to liver injury or hypersensitivity
Suggested Actions, Monitoring and Follow up Assessments	
Actions	

 Immediately discontinue study intervention Report the event to the sponsor within 24 hours Complete the [CRF as per CRF completion guidelines] and complete an SAE data collection tool if the event also met the criteria for an SAE² Perform follow-up assessments as described in the Follow up Assessment column Monitor the participant until liver chemistry test abnormalities resolve, stabilize, or return to baseline (see MONITORING) 
MONITORING:
 
If ALT[or AST]- $\geq 3 \times$ ULN AND total bilirubin $\geq 2 \times$ ULN (or at least a doubling of direct bilirubin in known Gilbert's syndrome) or INR > 1.5 (if measured):
 
 Repeat liver chemistry tests (include ALT, aspartate transaminase [AST], alkaline phosphatase, total and direct bilirubin and INR) and perform liver event follow-up assessments within 24 hours 	
 Viral hepatitis serology⁴ Obtain blood sample for pharmacokinetic (PK) analysis after the most recent dose⁵ Obtain a serum creatine phosphokinase (CPK) and lactate dehydrogenase (LDH) Fractionate bilirubin Obtain complete blood count with differential to assess eosinophilia Record the appearance or worsening of clinical symptoms of liver injury, or hypersensitivity [CRF as per CRF completion guidelines] Record use of concomitant medications (including acetaminophen, herbal remedies, recreational drugs, and other over-the-counter medications) Record alcohol use on the [Relevant Substance use tobacco CRF as per CRF completion guidelines] 
If ALT $\geq 3 \times$ ULN AND total bilirubin $\geq 2 \times$ ULN (or at least a doubling of direct bilirubin in known Gilbert's syndrome) or INR > 1.5 (if measured) obtain the


 Monitor participant twice weekly until liver chemistry test abnormalities resolve, stabilize, or return to baseline A specialist or hepatology consultation is recommended 
For all other criteria
 
 Repeat liver chemistry tests (include ALT, AST, alkaline phosphatase, total bilirubin and INR) and perform liver chemistry follow-up assessments within 24 to 72 hours Monitor participants weekly until liver chemistry abnormalities resolve, stabilize, or return to baseline 
RESTART
 
 Do not restart/rechallenge participant with study intervention. 	
following in addition to the assessments listed above:
 
 Anti-nuclear antibody, anti-smooth muscle antibody, Type 1 anti-liver kidney microsomal antibodies, and quantitative total immunoglobulin G (IgG) or gamma globulins Liver imaging (ultrasound, magnetic resonance, or computerized tomography) to evaluate liver disease; complete [CRF as per CRF completion guidelines] Liver biopsy may be discussed with local specialist if available, for instance: 
 In patients when serology raises the possibility of autoimmune hepatitis (AIH) In patients when suspected DILI progresses or fails to resolve on withdrawal of study intervention In patients with acute or chronic atypical presentation: hepatic vascular disorder, chronic hepatitis fibrosis, micro vesicular statosis If liver biopsy conducted complete (CRF as per CRF completion guidelines).
--	--

1. Serum bilirubin fractionation should be performed if testing is available. If serum bilirubin fractionation is not immediately available, stop study intervention if ALT [or AST] $\geq 3 \times \text{ULN}$ and total bilirubin $\geq 2 \times \text{ULN}$. Additionally, if serum bilirubin fractionation testing is unavailable, **record the absence/presence of detectable urinary bilirubin on dipstick** which is indicative of direct bilirubin elevations suggesting liver injury.
2. All events of ALT [or AST] $\geq 3 \times \text{ULN}$ and total bilirubin $\geq 2 \times \text{ULN}$ (or at least a doubling of direct bilirubin for known Gilbert's syndrome) or ALT [or AST] $\geq 3 \times \text{ULN}$ and INR > 1.5 may indicate severe liver injury (**possible 'Hy's Law'**) and must be reported to sponsor in an expedited manner and as an SAE if SAE criteria met (**excluding studies of hepatic impairment or cirrhosis**). The INR stated threshold value will not apply to participants receiving anticoagulants.
3. New or worsening symptoms believed to be related to liver injury (such as fatigue, nausea, vomiting, right upper quadrant pain or tenderness, or jaundice) or hypersensitivity (such as fever, rash, or eosinophilia).
4. Includes: hepatitis A immunoglobulin M (IgM) antibody; HBsAgG and HBcAB; hepatitis C RNA; cytomegalovirus IgM antibody; Epstein-Barr viral capsid antigen IgM antibody (or if unavailable, heterophile antibody or monospot testing); and hepatitis E IgM antibody. In those with underlying chronic hepatitis B at study entry (identified by positive hepatitis B surface antigen) quantitative hepatitis B DNA and hepatitis delta antibody. If hepatitis delta antibody assay cannot be performed, it can be replaced with a polymerase chain reaction (PCR) of hepatitis D RNA virus (where needed) [Le Gal, 2005].
5. Record the date/time of the PK blood sample draw and the date/time of the last dose of study intervention prior to the PK blood sample draw on the CRF. If the date or time of the last dose is unclear, provide the participant's best approximation. If the date/time of the last dose cannot be approximated OR a PK sample cannot be collected in the time period indicated above, do not obtain a PK sample. Instructions for sample handling and shipping are in the Study Reference Manual.

Liver Chemistry Increased Monitoring Criteria and Actions with Continued Study Intervention	
Criterion	Actions
ALT or AST \geq 3xULN and <5xULN and total bilirubin <2xULN or INR<1.5, without symptoms believed to be related to liver injury or hypersensitivity, and who can be monitored weekly for 4 weeks	
 Notify the Sponsor within 24 hours of learning of the abnormality to discuss participant safety Participant must return weekly for repeat liver chemistry tests (ALT, AST, alkaline phosphatase, total bilirubin) until the abnormalities resolve, stabilize, or return to baseline If at any time, the participant meets liver chemistry stopping criteria, proceed as described in Section 7.1. If, after 4 weeks of monitoring, ALT or AST<3xULN and total bilirubin <2xULN, monitor participants twice monthly until liver chemistry tests resolve, stabilize, or return to baseline.

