Potential Risks of Clinical Significance	Summary of Data/ Rationale for Risk	Mitigation Strategy
	
temporal relationship of the event to guselkumab exposure, and the exclusion of alternative etiologies, this event may represent drug-induced liver injury possibly related to guselkumab. Transaminase increases have been identified as an adverse reaction of guselkumab. In PsA studies transaminase increases were observed with a higher incidence with a maintenance dose of 100 mg every 4 weeks compared to 100 mg every 8 weeks.
	
jaundice), should undergo a thorough investigation for possible causes of liver injury. A participant must have their study intervention discontinued if the participant has severe liver test abnormalities that are not transient and are not explained by other etiologies (Section 7.1).

Immunosuppression	
Although guselkumab has been studied with other immunosuppressives in other diseases, there may be an increased risk of infection or malignancy.
	
In order to minimize the theoretical increased risk of infection or malignancy with the combination of guselkumab with immunosuppressive therapy, the baseline dose of oral GCs on study entry is limited to \leq60 mg/day prednisone or equivalent, which must be tapered starting at Week 1. Additionally, participants are also excluded from the study if they have received a variety of immunomodulatory therapies if received within a protocol defined timeframe from first study intervention (Section 5.1 and 5.2).

Risks Due to Study Procedures		

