- The participant has a serious adverse reaction that is related to an injection resulting in bronchospasm with wheezing and/or dyspnea that requires ventilatory support OR that results in symptomatic hypotension with a decrease in systolic blood pressure >40 mm Hg or blood pressure $<90/60$ mm Hg
- The participant has a reaction resulting in myalgia and/or arthralgia with fever and/or rash (suggestive of serum sickness and not representative of signs and symptoms of other recognized clinical syndromes) occurring 1 to 14 days after an injection of study intervention. These may be accompanied by other events including pruritus, facial, hand, or lip edema, dysphagia, urticaria, sore throat, and/or headache

- The participant has a malignancy including squamous cell skin cancer. Consideration may be given to allowing participants who develop ≤ 2 basal cell skin cancers that are adequately treated with no evidence of residual disease to continue to receive study intervention
- Participant requires dialysis
- Noncompliance with study drug administration defined as multiple episodes of missing the window in which to receive study intervention
- The participant has severe liver test abnormalities that are not transient and are not explained by other etiologies, as described in Section 10.9.
- In the LTE period, the study intervention must be discontinued if a participant experiences a GCA flare. Participants that experience a flare should have a Flare visit with assessments performed according to the SoA preferably within 1 week of having the flare and an early termination visit approximately 12 weeks after the last dose.
- After the study has been unblinded at the Week 60 DBL, participants in the LTE will be unblinded to treatment. Study treatment of participants on placebo will be discontinued. They may continue in the study for their planned visits as per the schedule of events until Week 112 or, in case of a GCA flare, until the early termination visit.

Discontinuation of a participant's study intervention should be considered under the following conditions:

- Worsening of GCA based on visual symptoms related to GCA
- If the participant initiates treatment with prohibited therapies for GCA, the medical monitor or designee should be contacted to discuss possible discontinuation of study intervention
- The participant develops a serious infection, including but not limited to sepsis or pneumonia

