5.1. Inclusion Criteria	Modified inclusion criterion 6 to accommodate update to criterion 4 from amendment 1.	Updated to provide clarification.
5.2. Exclusion Criteria	Modified exclusion criterion 22 to include "Within 3 months of first study intervention or at least 5 half-lives (whichever is greater)" for hydroxychloroquine, cyclosporine A, azathioprine, tacrolimus, sirolimus, sulfasalazine, leflunomide with cholestyramine washout or mycophenolate mofetil/mycophenolic acid.	To accommodate an HA request, safety measure, and protocol clarification, because wash-out period of 6 weeks may not always be sufficient.
6.8.2. Prohibited therapies	Added 'use of' and 'for GCA' to oral glucocorticoids (GCs).	Updated to provide clarification (limited use for other indications was not prohibited).
6.8.2. Prohibited therapies	Added 'until end of study' to intramuscular, intra-articular, intrabursal, epidural, intra-lesional, or IV GCs subsection.	Updated to provide clarification.
6.8.3. Rescue Medication	Languages changed from "the participant should continue" to "the participant may continue" plus added additional explanation on the follow-up procedures.	Updated to allow the investigator to decide whether a participant that has a flare should continue on study agent given there are alternative treatments other than GC such as tocilizumab. Additionally, updated to accommodate an HA request.
	Deleted the paragraph on the posttreatment phase.	To avoid duplication and because the paragraph should not be part of the Section 6.8.3. Rescue Medication.
7.1. Discontinuation of Study Intervention	Clarification of discontinuation criterion regarding TB: replacement of "is deemed ineligible" by "becomes ineligible".	To correct the language.
7.1. Discontinuation of Study Intervention; 10.2. Appendix 2: Clinical Laboratory Tests;	
 Removed the liver function tests results that will lead to discontinuation but instead and refer only to the Section 10.9 which now contains both alanine aminotransferase (ALT) and aspartate aminotransferase (AST) evaluations. 	
 To not duplicate criteria for treatment discontinuation that are presented and updated in Section 10.9 to avoid misinterpretation.

Section Number and Name	Description of Change	Brief Rationale

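### Liver appendix: the continued-dosing row joins bilirubin and INR with OR and so overlaps the stopping table, and Section 7.1 adds qualifiers that several stopping rows lack

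*Protocol*

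**What the plan says.** All references are to the Protocol.

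- **Continued dosing (Section 10.9, increased-monitoring table).** At ALT or AST ≥3 and <5×ULN, without symptoms and with weekly monitoring possible for 4 weeks, dosing continues if "total bilirubin <2xULN or INR<1.5".
- **Stopping (Section 10.9, stopping criteria).** With ALT or AST ≥3×ULN, the drug stops for total bilirubin ≥2×ULN ("or at least a doubling of direct bilirubin in known" Gilbert's syndrome). A separate row stops it for ALT or AST ≥3×ULN "and international normalized ratio (INR) > 1.5, if INR measured". Other rows stop it at ≥8×ULN, for related symptoms, when monitoring is impossible, and for persistence (5 to <8×ULN for at least 2 weeks, 3 to <5×ULN for at least 4 weeks). The action is immediate discontinuation, and the restart entry bars rechallenge.
- **Override (same row as the first item).** "If at any time, the participant meets liver chemistry stopping criteria, proceed as described in Section 7.1".
- **Section 7.1.** Discontinuation is mandatory for "severe liver test abnormalities that are not transient and are not explained by other etiologies, as described in Section 10.9". The Section 2.3.1 risk table has the same condition: "severe liver test abnormalities that are not transient and are not explained by other etiologies (Section 7.1").
- **Algorithm footnote (Section 10.9).** At ≥5×ULN with another etiology, dosing may be interrupted for more than 2 weeks and restarted after investigator and sponsor assessment. Discontinuation after 2 weeks at that level is tied to a judgement that the drug is responsible.

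**The concern.** A stopping rule that fires when either of two tests is abnormal has as its complement that both are normal. The continued-dosing row should therefore say *and*. With *or*, one participant can satisfy the written conditions for continuing and for stopping at the same visit.

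The override settles that conflict in favor of stopping, but it points to a bullet whose words are narrower than the stopping table. A site that reads Section 7.1 by itself could ask whether a single high value is lasting, or whether something else explains it, before stopping. Four kinds of stopping row do not ask those questions.

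This matters because the protocol names the risk. Section 2.3.1 describes a case of possible drug-induced liver injury and reports more transaminase increases with 100 mg every 4 weeks than every 8 weeks; this trial gives 200 mg every 4 weeks. Section 2.1 lists mild transaminitis as common in the disease itself, so an argument from another etiology is foreseeable. Inclusion criterion 15 admits ALT or AST up to 3×ULN, right at the row's threshold.

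**Working it through.** No sample size or error rate is involved, so the check is a truth table followed by a comparison of texts.

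**Step 1: overlap as written.** Take ALT at 4×ULN, a first value, no symptoms, weekly monitoring possible, no Gilbert's syndrome, no anticoagulant. Stop = (bilirubin ≥2×ULN) or (INR measured and >1.5). Continue, as written = (bilirubin <2×ULN) or (INR measured and <1.5).

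| Bilirubin (×ULN) | INR | Stop | Continue as written | Both |
|---|---|---|---|---|
| 1.0 | 1.1 | no | yes | no |
| 1.0 | 1.8 | yes | yes | **yes** |
| 2.5 | 1.1 | yes | yes | **yes** |
| 2.5 | 1.8 | yes | no | no |
| 1.0 | not measured | no | yes | no |
| 2.5 | not measured | yes | no | no |

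INR measured: 2 of 4 overlap. INR not measured: 0 of 2.

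**Step 2: can the overlapping cells occur?** Section 10.2 schedules INR at screening only. The row's own panel leaves it out: "Participant must return weekly for repeat liver chemistry tests (ALT, AST, alkaline phosphatase, total bilirubin"). The visible appendix text orders INR only among the actions that follow stopping. Note 2 removes the INR threshold for participants on anticoagulants. The overlap therefore needs an INR obtained outside the schedule in someone not anticoagulated. The cell with bilirubin 2.5 and INR 1.1 also needs the INR in hand no later than the bilirubin; otherwise the drug has already been stopped and restart is barred.

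**Step 3: does *and* repair it?** Replace the criterion by (bilirubin <2×ULN) and (INR not measured, or ≤1.5). Overlap becomes 0 of 4 and 0 of 2, and every cell is assigned. The sign matters: with *and INR <1.5*, a participant with bilirubin 1.0 and INR exactly 1.5 would fall in neither rule, because stopping needs INR >1.5.

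**Step 4: known Gilbert's syndrome with doubled direct bilirubin.** This is always a stop. As written, 3 of 4 cells overlap with INR measured and 1 of 2 without. Changing only *or* to *and* leaves 1 of 4 and 1 of 2. Repeating the Gilbert's clause in the row brings both to 0.

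**Step 5: Section 7.1 against the stopping table.** Persistence is in two stopping rows (5 to <8×ULN and 3 to <5×ULN), so the 7.1 wording partly matches. The ≥8×ULN, bilirubin, INR and symptomatic rows carry neither a persistence nor an etiology condition. Example: one ALT of 8×ULN with a suspected other cause is an immediate stop in Section 10.9 but does not plainly meet the 7.1 bullet. Scheduled chemistry can produce that value.

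**Step 6: footnote against stopping and restart rows.** Take ALT 6×ULN for at least 2 weeks with another etiology. The footnote permits continued interruption and later restart. The stopping row requires discontinuation, and the restart entry forbids rechallenge. Both cannot be followed. The conflict is confined to 5 to <8×ULN, at least 2 weeks, another etiology.

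**The case against.** The best defense is that every overlapping cell already ends in stopping. The override sits in the same row, Section 7.1 opens by making discontinuation mandatory, the stopping table orders it without needing any pointer, and note 1 says the same for bilirubin. The sponsor is told within 24 hours on either route. This stands, and it is why the severity is low.

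A reader might infer that Sections 10.9 and 7.1 refer to each other in a circle and leave the action undefined. The documents do not support that: Section 7.1 supplies the action, Section 10.9 supplies the criteria, and the stopping table is complete by itself.

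A reader might also infer that Section 7.1 is a separate, weaker rule. It is not: its bullet defers to Section 10.9, and the Amendment 2 entry in Section 10.12 (used here for intent only) gives the aim as "To not duplicate criteria for treatment discontinuation that are presented and updated in Section 10.9 to avoid misinterpretation". The defense is also right that persistence appears in two stopping rows and another etiology in the footnote. What it does not answer is that the other four kinds of row have neither condition, so the bullet is an inaccurate summary of them.

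Finally, the footnote conflict concerns participants whose dosing is already interrupted, with sponsor assessment before any restart. That limits the harm but does not reconcile the two instructions.

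**Conclusion.** The text is wrong as written, with low severity. The *or* creates a logical overlap in 2 of 4 combinations when INR is measured and in none when it is not, outside known Gilbert's syndrome. These are counts of combinations, not event rates, and it would be wrong to infer that participants meeting the bilirubin or INR stopping criteria are meant to stay on drug.

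The two conflicts reachable with routine chemistry have more practical weight: the Section 7.1 and 2.3.1 qualifiers set against unqualified stopping rows, and the footnote's restart option set against the stopping and restart rows. No endpoint, analysis or sample size is affected.

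The conclusion assumes the tables carry the operative rule. The appendix's two algorithm figures are not visible in the text available for review and may already show the correct logic.

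**What to change.** 1. **Row criterion.** *Total bilirubin <2×ULN (with no doubling of direct bilirubin if Gilbert's syndrome is known) and INR ≤1.5 (if measured; not applied to participants receiving anticoagulants).*
2. **Override.** Send the site to the stopping actions in Section 10.9 instead of to Section 7.1.
3. **Section 7.1 bullet and Section 2.3.1 cell.** At the next amendment, replace the qualified wording with *meets the liver chemistry stopping criteria in Section 10.9*.
4. **5 to <8×ULN for at least 2 weeks with another etiology.** The sponsor's safety physicians should choose one rule. If they keep the footnote (Section 10.12 records that a footnote on interruption in this range was added at a health authority's request), any exception in the restart entry must be limited to this case. It must not reach the ≥8×ULN, bilirubin, INR or symptomatic criteria. If they prefer the stricter rule, they should delete the footnote's extended-interruption sentence.
5. **Figures.** Check both algorithms against the final wording.

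Items 1 and 2 restate existing intent and could go out first as a protocol clarification communication under Section 10.3. Items 3 and 4 alter the wording of a mandatory discontinuation rule and belong in an amendment. The cost is a few lines of text, with no change to visits, endpoints or sample size.
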